### 7.3 Participant Recruitment, Information and Consent

Written information and advertisements approved by the IRB may be used for recruitment purposes. Individuals treated at MGH, BWH, other Harvard University CFAR-associated institutions, and other hospitals in the Boston area, such as Fenway Health, Tufts Medical Center, and the Boston Medical Center, are permitted to participate; all possible candidates will be referred to MGH for evaluation and possible study participation. Eligible study participants may receive an invitation to participate in the study if the participant has previously agreed to be contacted in such matters. Invitation may also be provided as part of routine medical visits to the Department of Infectious Diseases at MGH, the MGH Clinical Trials Unit or BWH, or to other hospitals. Interested participants can contact the primary Investigator or study nurse to receive written information and schedule an appointment for further information, possibly attended with a companion. If the participant then wishes more time to consider participation in the study, presence of a companion, or repetition of information, a new appointment will be scheduled for this.

Individuals from investigators' own clinics are also potentially eligible for this study. Patients of the investigators will be informed of the study by participant summary sheets or one of the co-investigators (who do not serve as the patient's primary physician). A study co-investigator distinct from the patient's primary physician will conduct the informed consent process with interested patients from the investigators' clinics.

Individuals who participated in stage 1 or 2 are permitted to take part in stage 3 if they have not experienced a (clinical or laboratory) grade 3 or 4 adverse events during stage 1 or 2.

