### 3.0 SCHEMA

**A Phase I-II pilot study to assess the safety and efficacy of combined administration with pegylated IFN- $\alpha$ 2a and the histone deacetylase inhibitor (HDACi) panobinostat for reducing the reservoir of HIV-1 infected cells in cART-treated HIV-1 positive individuals.**

**DESIGN:** This study is a prospective, open-label, randomized, two-arm, dose-escalation exploratory pilot clinical trial involving HIV-1 infected participants treated with suppressive combination antiretroviral therapy (cART).

**DURATION:** One month of pre-treatment observation, one week of treatment, three weeks of post-treatment observation. The total duration per patient will be 2 months.

**SAMPLE SIZE:** n=8 participants for stage 1 and stage 2; n=18 in stage 3 (total of 34 individuals)

**POPULATION:** Participants (18-65 years of age) with HIV-1 infection who have received antiretroviral therapy (ART) with HIV RNA levels <50 copies/mL for at least two years and a CD4 T cell count >400 cells/mm^3. Patients who started antiretroviral treatment in early HIV-1 infection (within <12 months of HIV-1 transmission), and patients who started antiretroviral treatment in chronic infection ( $\geq$ 12 months after HIV-1 transmission) are eligible for this study.

**REGIMEN:** All study patients will receive the histone deacetylase (HDAC) inhibitor panobinostat administered as an oral tablet three times every other day (TIW) during the treatment week.

In stage 1, each panobinostat dose will be 5 mg; in stage 2, each panobinostat dose will be 10 mg; in stage 3, each panobinostat dose will be 15 mg.

In each stage, participants will be randomized to one of the following regimens:

**Arm A:** Treatment with panobinostat alone at stage-specific dose (n=2 participants in stages 1 and 2; n=4 participants in stage 3).

**Arm B:** Combined treatment with panobinostat (at the stage-specific dose) and pegylated IFN- $\alpha$ 2a (Pegasys, 180 micrograms, administered by s.c. injection simultaneously with the first dose of panobinostat during the treatment week (n=6 participants in stages 1 and 2; n=10 participants in stage 3).

**Arm C:** Treatment with pegylated IFN- $\alpha$ 2a only (Pegasys, 180 micrograms, administered by s. c. injection; n=0 in stage 1/2, n=4 in stage 3)

Progression to stages 2 and 3 will depend on satisfactory safety reviews of data from the preceding stage.

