Pregnancy testing 	X	X	X					X
Hep B/C serologies, PPD/TB Spot PT, PTT	X							
Eye exam	X		X					
Stress echocardiogram/dobutamine stress test	X							
HIV antibody	X							
Differential blood count and CD4/CD8 T cell counts	X	X	X			X	X	X
Plasma HIV-1 RNA	X		X	X		X	X	X
Complete/targeted physical exam	X	X	X			X	X	X
Panobinostat PK			X	X		X	X	
ECG	X		X	X		X		
Histone acetylation levels		X	X	X		X	X	X
HIV-1 DNA		X	X			X	X	X
Viral outgrowth assays		X					X	
CD4 T cell -associated HIV-1 RNA		X	X	X		X	X	X
HIV-1 DNA in CD4 T cell subsets		X					X	
Immune phenotyping		X	X	X		X	X	X
Functional immune assays		X		X		X	X	
Gene expression profiling		X					X	

Immune activation markers		X		X		X	X	

Table 1: Schedule of events during the study. (*blood draws on this day will occur 6h after administration of study drug). CBC includes WBC, RBC, PLT, Hgb, Hct, MCV, MCH, RDW, MCHC, MPV. Liver function tests include AST/ALT, TBili, DBili, Albumin. Chemistry levels include Na, K, Cl, HCO3, BUN, Crea, Glucose, Mg. Women of childbearing potential only. †Number reflects time interval during which study visit should occur from Study Entry.
								

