### 9.3.3 Treatment phase

Study entry will be defined as the day on which the first dose of study drug is administered (day=0, visit V3).

On this day, participants will have the following procedures performed:

- Perform a pregnancy test, ECG and vital signs/physical exam (including eye exam), as described in pre-treatment assessment (9.2.4).
- Review concomitant medications.
- Collect blood for baseline immunologic and virologic assays.
- Perform randomization to treatment Arm A or B or C.
- After the above procedures are completed, administer one s.c. dose of PEG-IFN- $\alpha$ 2a in patients randomized to treatment Arm B and C.
- Immediately after the first administration of PEG-IFN- $\alpha$ 2a, participants will be asked to take the first pill of panobinostat p.o., at the stage-specific dose if randomized to arm A or B.
- At 6h after administration of panobinostat, blood samples will be collected for virological, immunological and pharmacokinetic assays.
- 4-6 hours after administration of panobinostat, at the time of Cmax for panobinostat, a 12-lead ECG will be performed.
- On discharge, participants randomized to stage A or B will receive two more stage-specific panobinostat doses and will be instructed to take them in the mornings of study day 2 and day 4.

On Day 2, participants will be called by phone by one of the study investigators to discuss possible side effects. Participants will return on Day 4, six hours after administration of the third dose of panobinostat (visit V4), for collection of blood samples for virological, immunological and gene expression studies, as described in Table 1, and for an ECG. The full volume of blood to be collected on day 4 will only be collected if the most recently available hemoglobin level is  $\geq 12.0$  g/dL for men and hemoglobin  $\geq 11.0$  g/dL for women.

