#### 11.2 Grade 2 adverse events

Participants experiencing grade 2 AE(s), which the patient believes is/are tolerable and in the Investigators' judgment is/are acceptable, may continue treatment at the current dose and schedule. More frequent patient monitoring may be required, and participants must be informed to contact the Investigators immediately if there is any worsening of symptoms. If a patient experiences new (or treatment emergent) grade 2 AE(s) considered at least possibly related to the study medication, and which the patient finds intolerable or in the Investigators' judgment is/are not acceptable, treatment must be held until the AE(s) resolves to grade  $\leq 1$ . Study treatment may then be restarted at the same dose and schedule. If the same intolerable grade 2 AE(s) occurs again, the study treatment must again be temporarily discontinued until the toxicity resolves to grade  $\leq 1$ . At the discretion of the Investigators, participants with repeated grade 2 AEs of major organs (e.g. heart, lungs, CNS) may be discontinued from further study treatments.

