### 11.4 Specific management of panobinostat and PEG-IFN- $\alpha$ 2a toxicity

#### 11.4.1 Diarrhea

Diarrhea is a recognized side effect of panobinostat, although the frequency of diarrhea with low-dose panobinostat is expected to be low. Each patient should be instructed to have loperamide readily available and to begin treatment for diarrhea at the first episode of poorly formed or loose stools or the earliest onset of bowel movements more frequent than normally expected for the patient.

TOXICITY		ACTION
Thrombocytopenia	Grade 2 (PLT 50,000-99,999/ul)	Discontinue dosing.
	Grade 3 (PLT < 50,000/ul)	
	Grade 4 (PLT < 25,000/ul) or	
Neutropenia	Grade 1 (ANC 800-1000/ul)	none
	Grade 2 (ANC 600-799/ul)	If ANC > 750/ul, patient may continue study drugs If ANC < 750/ul, discontinue dosing permanently
	Grade 3 (ANC 400-599/ul)	Discontinue dosing permanently.
	Grade 4 (ANC < 400)	

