### 11.4.3 Hematologic toxicity

Both PEG-IFNa2a and panobinostat can cause hematologic toxicity. Hematologic toxicity during the study should be managed per Table 3.

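### Read literally, section 7.3 lets a participant re-enter at stage 3 after a permanent dosing stop for ANC 600-749/ul, because its bar starts at grade 3

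*Combined protocol and SAP*

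**What the plan says.** Section 7.3 allows people treated in stage 1 or 2 to join stage 3. They are "permitted to take part in stage 3 if they have not experienced a (clinical or laboratory) grade 3 or 4 adverse events" during their first participation. It names no other toxicity condition for re-entry.

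Table 3 (section 11.4, management of hematologic toxicity) has a row "Grade 2 (ANC 600-799/ul" and splits the action inside that row. Above 750/ul the participant may stay on the study drugs. Below that value the instruction is "If ANC < 750/ul, discontinue dosing permanently". Grade 3 in the same table is ANC 400-599/ul.

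Section 11.4.3 states that "Both PEG-IFNa2a and panobinostat can cause hematologic toxicity" and sends hematologic toxicity arising in the study to Table 3. The schema (section 3.0) gives panobinostat doses of 5 mg in stage 1 and 10 mg in stage 2, and "in stage 3, each panobinostat dose will be 15 mg".

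**The concern.** The two rules use different thresholds for what looks like one decision: whether a person may receive study drug again. Table 3 treats an ANC of 600-749/ul as serious enough to end dosing for good. Section 7.3 looks only at grade, so it does not see that event. Anyone screening for stage 3 with 7.3 as the re-entry rule would find the participant admissible.

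What is at stake is the safety of a small number of people. Every stage 3 arm contains at least one of the two drugs that the protocol names as able to cause this toxicity, and most stage 3 places carry a higher panobinostat dose than the person had before. The efficacy analysis is not affected.

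**Working it through.** The plan states no figure on this point, so the check compares rules and then does simple arithmetic on dose and allocation.

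**1. The gap.**
- Permanent stop (Table 3): ANC below 750/ul.
- Barred from re-entry (7.3, using the Table 3 grades): grade 3 or 4, so ANC below 600/ul.
- Stopped but not barred: ANC 600-749/ul, a band 750 - 600 = 150/ul wide.

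**2. Does another written rule close it?**
- 7.1.10 and 9.2.4 require ANC of at least 1500/mm3 at screening and before dosing. They test the current count, so a recovered participant passes.
- 7.2.20 excludes a history of anaphylaxis, allergy or serious reactions. A non-serious grade 2 laboratory fall is none of these.
- 10.8 lists hypersensitivity and pregnancy as the absolute contraindications.
- 12.1.2 names related grade 3 or 4 events. Beyond those, its relevant entries rest on investigator or adviser judgement.
- 7.2.11 and 7.2.17 could exclude the person, but only if the investigator so judges.
- 10.9 requires review of all safety data before the next stage opens. Its listed escalation criteria count related events of grade 3 or above and cardiac ischemia. It decides whether the stage proceeds, not whether a given person may re-enter.

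None of these is a fixed bar for the 600-749/ul band.

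**3. Where the stop can act.** Panobinostat is taken on days 0, 2 and 4, and peginterferon once on day 0. In Table 1 the row "Differential blood count and CD4/CD8 T cell counts" has post-dose entries on days 4, 10 and 28 only, and the day 4 visit takes place "six hours after administration of the third dose of panobinostat". If dosing runs on time and no extra count is taken, no post-dose count precedes a remaining dose in that stage. The later dosing that the protocol provides for is stage 3 re-entry, so that is where the stop would mainly matter.

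**4. Exposure on re-entry.**
- Dose ratio from stage 1: 15/5 = 3.0. From stage 2: 15/10 = 1.5.
- Stage 3 allocation is 4 (Arm A), 10 (Arm B) and 4 (Arm C), total 18. Places with panobinostat 15 mg: (4 + 10)/18 = 14/18 = 78%. Places with peginterferon only: 4/18 = 22%.
- Planned pool of possible re-entrants: 8 + 8 = 16. Section 7.3 sets no cap on how many may return.

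The documents give no rate for ANC 600-749/ul under the combination, so no probability of such a case is calculated.

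**The case against.** The strongest reply is that the texts can be read together. Section 7.3 states a condition for re-entry and does not claim to override dosing rules. Section 11.4.3 places hematologic toxicity in the study under Table 3, so a permanent stop plausibly lasts through all stages, and 7.3 adds a separate bar for grade 3 and 4 events. This is a fair reading, and probably the intended one. It does not remove the problem: on that reading 7.3 admits a person who may not be dosed, and anyone applying 7.3 literally would dose that person.

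Four stronger readings are tempting, and the documents do not support them.
- *The rules flatly contradict each other.* A reader might infer this, but 11.4.3 offers a way to reconcile them. The defect is that 7.3 does not say so.
- *Section 7.3 is the only safeguard.* It is not. Under 10.9 all safety data go to the internal and external committees, the IRB and the FDA before stage 3. In addition, 7.2.11 covers conditions that the study drugs might worsen, and 7.2.17 covers conditions that might put the participant at risk.
- *Section 11.2 reopens the matter*, because for grade 2 events it says "Study treatment may then be restarted at the same dose and schedule". For ANC, 11.4.3 already points to Table 3, so 11.2 needs no change on this account.
- *Every re-entrant gets more panobinostat.* Arm C, with 4 of 18 places, gets none.

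The schedule argument also has limits. Doses can be delayed (10.8) or held (11.2), and extra counts can be taken, so the stop can act within a stage. On scheduled draws the grade 3 and 4 neutrophil stops would be just as idle. The timing shows where the rule matters; it does not prove a conflict.

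The event may also never occur. Section 5.4.3.1 reports normal neutrophils in all 15 participants of the previous 20 mg panobinostat study, although that study did not include peginterferon.

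**Conclusion.** The inconsistency is real and minor. A participant with ANC 600-749/ul in stage 1 or 2 meets a permanent stop rule in Table 3 and is not excluded by 7.3. An unsafe re-entry would need several things together: such a count, recovery to at least 1500/mm3, a wish to return, and an investigator who neither carries the Table 3 stop forward nor uses the discretionary exclusions. That is unlikely, but no fixed rule prevents it. If it happened, the person would be randomized in a stage where 14 of 18 places give 15 mg panobinostat, 1.5 to 3 times the previous dose.

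The conclusion rests on the wording of 7.3 and Table 3 as printed and on using the Table 3 grades for ANC. It assumes no event rate.

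**What to change.** Add one clause to 7.3: anyone who met a permanent-discontinuation criterion in Tables 2-4 during stage 1 or 2 may not take part in stage 3. This brings the re-entry rule into line with Table 3 and with 11.4.3, and replaces reliance on discretion with a fixed rule.

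The change needs no new visit, test or participant. Its cost is that a few people whose counts have recovered would be lost as stage 3 re-entrants.

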### 7.4 Study participant replacement

In stage 1 and 2, up to two participants dropping out of the study prior to study completion will be replaced by a new study subject. If, however, the subjects discontinue the study due to safety or tolerability concerns, the subjects will not be replaced. In stage 1, 2 and 3, all participants dropping out of the study prior to initiation of the first dose of the study medication will be replaced.

### 7.5 Randomization

Participants will be randomized to treatment Arm A or treatment Arm B or treatment Arm C (in stage 3 only). Participants in treatment Arm A (n=2 participants in stage 1 and 2; n=4 participants in stage 3) will receive treatment with panobinostat only, and participants in treatment Arm B (n=6 participants in stage 1 and 2; n=10 participants in stage 3) will receive combined treatment with panobinostat and pegylated IFN- $\alpha$ 2a. Participants in Arm C (n=4 in stage 3) will receive treatment with pegylated IFN- $\alpha$ 2a only.

Randomization will occur on day 0 of the study, prior to administration of the first dose of the study medication. Participants will be informed about the randomization decision, and open-label study medication will be administered.

## **8.0 STUDY TREATMENT**

### 8.1 Panobinostat

#### 8.1.1 Formulation

Panobinostat is a highly potent class I/II HDAC inhibitor belonging to the hydroxamic acid class of compounds. The drug product provided is an immediate-release solid oral dosage form tablet containing 5 mg panobinostat for stage 1, 10 mg panobinostat for stage 2, and 15 mg panobinostat for stage 3. For further details on physical, chemical and pharmaceutical properties refer to the Investigator's Brochure. The drug will be packed and labeled as investigational product in accordance with current guidelines and applicable regulatory requirements.

The Massachusetts General Hospital Pharmacy will be responsible for the import, labeling and storage of the investigational drug. The study Investigators or the study nurse will request the appropriate quantity of the investigational drug from the MGH Pharmacy prior to dispensing to study participants. The investigational drug will then be delivered with the required labeling containing batch number, manufacturing date and time, project name, contact person and drug ID number.

**Note:** Refer to the Investigator's Brochure for further information about panobinostat and its components.

### 8.1.2 Administration

Panobinostat will be orally administered as a 5 mg tablet (stage 1), a 10 mg tablet (stage 2, two 5 mg tablets can also be used) and a 15 mg tablet (stage 3, three 5 mg tablets can also be used) every second day during the treatment week (total of three oral doses). The first dose of panobinostat will be administered concomitantly to the corresponding subcutaneous injection of PEG-IFN- $\alpha$ 2a in Arm B.

The MGH Pharmacy will be responsible for secure and correct storage of the investigational drug until reception at the MGH Clinical Trials Unit, after which the Investigators will be responsible. The investigational drug will be clearly marked and stored in a locked medicine storage room at the MGH Pharmacy. Lists of received, used and remaining quantities of the investigational drug will be kept. Any discrepancies must be resolved.

### 8.1.3 Storage

Panobinostat will be clearly marked and stored in a locked medicine storage room at room temperature.

## 8.2 Peginterferon alfa-2a, (Pegylated interferon $\alpha$ -2a, Pegasys™)

### 8.2.1 Formulation

PEG-IFN- $\alpha$ 2a will be used in single-use vials for this study. Other excipients include benzyl alcohol, sodium chloride, sodium acetate trihydrate, acetic acid, polysorbate 80, and water. For further information about this product, refer to the FDA-approved package insert. PEG-IFN- $\alpha$ 2a will be obtained from Roche Laboratories by the MGH pharmacy in syringes containing 180mcg of the drug in 1ml. PEG-IFN- $\alpha$ 2a supplied by Roche in a single-use syringes containing 180mcg of the drug in 0.5ml is also acceptable. Commercially available PEG-IFN- $\alpha$ 2a, manufactured by Roche and provided as syringes containing 180mcg of the drug, can also be used.

### 8.2.2 Administration

180mcg of PEG-IFN- $\alpha$ 2a will be administered by subcutaneous injection once at the beginning of the treatment week in Arm B. One dose of IFN- $\alpha$ 2a will be given. Injection of IFN- $\alpha$ 2a will be given simultaneously with the first dose of panobinostat.

### 8.2.3 Storage

PEG-IFN- $\alpha$ 2a will be stored and refrigerated at 2° to 8° C (36° to 46° F) prior to dispensing.

## 8.3 Accountability of study medication

The study participants in Arm B will receive PEG-IFN- $\alpha$ 2a injections by study staff during their study visits. Panobinostat doses will be taken by participants in the clinic on day 0. The remaining tablets will be dispensed to participants and self-administered by participants at the scheduled time points.

## 8.4 Dosing schedule for investigational drugs:

The investigational drugs will be administered as summarized in Figure 1 and Table 1.

### 8.5 Monitoring for adherence to investigational drugs

The first dose of the panobinostat (in study arm A and B) and pegylated IFN- $\alpha$ 2a (in study arm B or C only) will be administered during admission to the hospital under direct observation by study nurses or physicians. Subsequent doses of panobinostat can be self-administered by patients at home, at pre-defined time points. Internet-based scheduling tools will be used to remind patients of taking panobinostat as scheduled, if patients agree to this procedure.

For each participant, received and remaining tablets of the investigational drugs will be accounted for during follow-up visits; results will be noted in the CRF. If non-adherence is suspected based on these evaluations, study staff will inform the protocol chairs and review the importance of adherence to all study medications with the participant and ongoing adherence support will be provided. The study chair may exclude a participant from continuing the study if there is evidence for a level of non-compliance with study medication that, in the investigators' judgments, may compromise study results.

### 8.6 Concomitant Medication

#### 8.6.1 Prohibited Medications

Participants will be excluded from the study if they are taking any of these medications during the course of this clinical trial:

- Systemic steroids up to 7.5 mg of Prednisone per day (or equivalent dose of alternative steroids); inhaled or nasal steroid therapy is also permitted
- Interleukins
- Systemic interferons other than the study medications
- Systemic chemotherapy
- Ritonavir, cobicistat or other similarly potent inhibitor of CYP3A4
- Grapefruit juice is a moderate to strong CYP3A inhibitor and may increase absorption and exposure to panobinostat. Therefore, participants will be instructed not to consume grapefruit juice during the study
- Pharmaceuticals that are strong or moderately strong CYP3A4 inhibitors, or CYP2D6 substrates with a narrow therapeutic window (see section 7.2.18 and 7.2.19)
- Drugs with a known potential to lead to QTc prolongation (see section 7.2.22)

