If the female participant cannot provide written proof of a male partner's vasectomy status, the verbal report of her partner's status should be written into the source documents.

- 7.1.20 Female participants of reproductive potential must refrain from participating in active attempts to become pregnant, and, if participating in sexual activity that could lead to pregnancy, the participant must agree to use at least two reliable forms of contraception that are non-estrogen based. All participants of reproductive potential must continue to use contraceptives for 90 days after completing panobinostat/IFN- $\alpha$ 2a treatment.

Acceptable forms of contraception include:

- Condoms (male or female) with or without spermicidal agent
- Diaphragm or cervical cap with spermicide
- Non-hormonal intrauterine device (IUD)
- Tubal ligation
- Non-estrogen containing formulations of hormonal birth control drugs, given by pills, shots, or placed on or under the skin, for at least 90 days prior to study entry

Providers and participants should be advised that not all contraceptive choices listed above can prevent HIV transmission and that some may actually increase the risk of HIV acquisition. Study participants who are sexually active with HIV negative or unknown HIV serostatus partners should be advised that they need to consider effective strategies for reducing the risk of HIV transmission, as well as meeting the requirement for effective contraception during their participation in the study. Study participants should discuss contraceptive choices and HIV risk reduction methods with their healthcare provider.

- 7.1.21 Female participants who are not of reproductive potential are not required to practice contraception.
- 7.1.22 Male study participants must use a condom during intercourse while taking panobinostat and for five half-lives (5x16h, total of 80 hours) after stopping treatment and should not father a child in this period. A condom is required to be used also by vasectomized men in order to prevent delivery of the drug via seminal fluid. The partners of patients should also use contraception to avoid pregnancy.
- 7.2 Exclusion Criteria
- 7.2.1 Confirmed HIV-1 RNA >50 copies/mL within 24 months of screening, except for a single blip of <400 copies/mL during the 24 months prior to screening.

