#### 8.6.4 Other concomitant medication

Any other current medical therapy either recorded at study entry or initiated during the study will be recorded in the CRF. Initiation of medical therapy that requires use of a drug specified in the exclusion criteria will result in withdrawal from the investigational drug. Medication entries should be specific to

trade name, the single dose and unit, the frequency and route of administration, the start and discontinuation date, and the reason for therapy.

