## Protocol

### 9.3.4 Post-treatment observation period

Participants will return for additional collection of blood samples for virological and immunological analyses on day 10 (visit V5) and 28 (visit V6) (see Table 1). Preceding each blood collection, the hemoglobin levels determined from the visit before (visit V4 and V5, respectively) will be used to assess the participant's ability to give blood. A minimum requirement of hemoglobin  $\geq 12.0$  g/dL for men and hemoglobin  $\geq 11.0$  g/dL for women will be used.

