### 9.5 Early termination visit

Any participant who discontinues study treatment prematurely should be encouraged to continue to participate in all scheduled visits.

A participant may voluntarily discontinue participation in this study at any time. The investigator may also, at his or her discretion, discontinue the participant from participating in this study at any time. If a participant is prematurely discontinued from participation in the study for any reason, the investigator must make every effort to perform the following evaluations:

- Perform clinical evaluation.
- Review adverse events and concomitant medications.
- Obtain samples for laboratory tests:
  - Hematology (CBC/differential), Chemistry testing.
  - HIV RNA testing by Roche Taqman Version 2.0 assay.
  - CD4 T cell counts.
  - Collection of blood samples for virological and immunological assays.

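### Sections 8.6.1 and 8.6.4 contradict each other on whether a prohibited medicine ends study participation or only study drug, and 8.5 adds a discretionary exclusion, so day-10 and day-28 data of treated participants can be lost after dosing is over

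*Combined protocol and SAP*

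**What the plan says.** **Prohibited medicines.** Section 8.6.1 introduces its list with "Participants will be excluded from the study if they are taking any of these medications during the course of this clinical trial". The list covers systemic steroids, interleukins, other interferons, chemotherapy, CYP3A4 inhibitors, CYP2D6 substrates with a narrow window, and QTc-prolonging drugs. Section 8.6.4 reads: "Initiation of medical therapy that requires use of a drug specified in the exclusion criteria will result in withdrawal from the investigational drug". Section 9.5 adds: "Any participant who discontinues study treatment prematurely should be encouraged to continue to participate in all scheduled visits". Section 12.1.2 likewise asks anyone who comes off drug after at least one dose to attend all later visits.

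**Non-compliance.** Section 8.5 says: "The study chair may exclude a participant from continuing the study if there is evidence for a level of non-compliance with study medication", where the investigators judge that the results could be compromised. The evidence comes from tablet counts: "received and remaining tablets of the investigational drugs will be accounted for during follow-up visits". The same section has the first panobinostat dose (arms A and B) and the PEG-IFN injection (arms B and C) given under observation. Repeated non-adherence is an example reason for leaving the study in 12.1.1 and for leaving the drug in 12.1.2.

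**Timing.** The first panobinostat dose is taken on day 0. For the other two, participants "will be instructed to take them in the mornings of study day 2 and day 4" (9.3.3). Visit V4 is six hours after the third dose. Visits V5 and V6 are on days 10 and 28.

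**Data use.** Sections 12.1.1 and 12.1.2 use data only up to the date of withdrawal, from study and from drug respectively. Section 14.4.3 limits the modified intention-to-treat efficacy set to treated participants with baseline and day-10 data, and leaves out those who discontinue study participation.

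**The concern.** Staff who learn that a participant has started a listed medicine have two instructions. One ends study participation; the other ends dosing and keeps the visits. Which one is followed decides whether outcome data exist.

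After day 4, as scheduled, no dose remains, so ending participation normally affects only the data. These are exclusions after randomisation, and they need not be balanced. A tablet-based judgement cannot arise in arm C, and the person who makes it knows the allocation. Some listed medicines could be started to treat an adverse event, which would tie the loss to treatment.

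Safety data are touched too. Section 10.5.2 closes adverse-event reporting at study discontinuation if that comes before 30 days after the last dose, while the escalation criteria in 10.9 count events up to day 28. In stage 3, 7.4 replaces only people who drop out before their first dose.

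**Working it through.** **1. The sections side by side.**

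| Event | Ends study participation | Ends study drug, visits continue |
|---|---|---|
| Listed medicine taken | 8.6.1 (mandatory wording, whole trial) | 8.6.4, with 9.5 and 12.1.2 |
| Non-adherence | 8.5 (discretionary), 12.1.1 | 12.1.2 |

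The overlap on medicines is large but not complete: 8.6.4 refers to the exclusion criteria, and 8.6.1 has its own list that partly cross-refers to them. One bullet conflicts outright. Section 8.6.1 lists systemic steroids up to 7.5 mg prednisone per day as prohibited; 7.2.21 permits that amount.

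**2. What an exclusion removes, by when it is made (schedule of 9.3.3 and Table 1).**

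- Up to day 4, arms A and B: any outstanding panobinostat doses, and the day-10 and day-28 values. In arm C no dose remains after day 0.
- Between the last dose and day 10: no dose; the day-10 and day-28 values.
- After day 10: no dose; the day-28 value. Section 12.1.1 would keep the day-10 value, but 14.4.3 read literally drops the participant from the efficacy analysis.

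The first tablet count is at V4, after the third dose if the schedule was kept. Following 8.6.4 instead does not by itself save the data: a participant withdrawn from drug before day 10 would attend, but 12.1.2 stops data use at the withdrawal date.

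**3. Power.** Inputs from 14.3: effect 0.82 log10, SD 0.436, one-sided Wilcoxon rank sum test, alpha 0.05, normal data, one loss allowed per arm (10/4/4 becomes 9/3/3). Method: take the largest critical value of U whose exact null probability is at most 0.05, then simulate 200,000 trials.

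| Arm B vs one control arm | Critical U | Exact alpha | Power |
|---|---|---|---|
| 9 vs 3 (the plan) | 4 | 11/220 = 0.050 | 80.1% |
| 10 vs 4 (no loss) | 7 | 38/1001 = 0.038 | 85.3% |
| 10 vs 3 (one control loss) | 4 | 11/286 = 0.038 | 76.9% |
| 9 vs 2 (two control losses, one in B) | 1 | 2/55 = 0.036 | 61.0% |
| 10 vs 2 (two control losses) | 1 | 2/66 = 0.030 | 58.7% |
| 9 vs 1 | none | smallest p = 1/10 | 0% |

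The stated 80% is reproduced. Pooling the controls (9 vs 6) gives 93.8%, so the stated figure refers to one control arm at a time. Power at 10 vs 3 is below that at 9 vs 3 because the attainable alpha is lower. At 9 vs 2 the effect detectable with 80% power rises from 0.82 to about 1.06 log10 (10^1.06 = 11.5-fold, against 10^0.82 = 6.6-fold).

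**4. How likely.** The documents give no rate. Assume an independent loss probability q per person. The chance of at least two losses among four is 1 − (1−q)^4 − 4q(1−q)^3:

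- q = 5%: 1 − 0.8145 − 0.1715 = 1.4%
- q = 10%: 1 − 0.6561 − 0.2916 = 5.2%
- q = 20%: 1 − 0.4096 − 0.4096 = 18.1%

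**The case against.** Several stronger readings are tempting, and the documents do not support them.

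- **That both rules always delete day-10 and day-28 outcomes without altering treatment.** Section 8.5 is discretionary. A trigger on days 0 to 4 in arms A and B can leave doses outstanding, and the day-2 call could reveal one. A non-complier may still hold tablets at V4, and 10.8 and 11.2 allow doses to be delayed or held. A removal after day 10 follows the primary sample.
- **That one exclusion cuts power from 80% to 61%.** The 80% already allows one loss per arm. One loss from a full control arm gives about 77%; about 61% needs two of the four controls.
- **That one exclusion in stage 1 or 2 costs one of the eight people on whom escalation rests.** Section 7.4 replaces up to two dropouts in those stages unless they left for safety or tolerability.
- **That the rule protects nothing from about day 7.3 (day 4 plus 80 hours).** The 80 hours come from the contraception clause, "for five half-lives (5x16h, total of 80 hours) after stopping treatment", and concern panobinostat alone. Section 5.5 describes PEG-IFN as circulating much longer than its parent compound, and listed immune-active drugs could affect the endpoints up to day 28.

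There are also partial safeguards. Section 9.5 asks for every effort to take virological samples when anyone leaves early. Section 10.7 follows recorded events to resolution or stabilisation, and 10.5.9 keeps attributable later serious events reportable. These limit the loss. They do not supply the scheduled day-10 and day-28 values, except where an early-termination sample happens to fall in a visit window, and they leave the contradiction between 8.6.1 and 8.6.4 in place.

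**Conclusion.** The contradiction between 8.6.1 and 8.6.4 is plain on the text. With the discretionary exclusion in 8.5, it allows treated, randomised participants to be removed from follow-up at a stage when, on the planned schedule, no treatment is left to change. Sections 12.1.2 and 14.4.3 enlarge the loss. A difference between arms is possible, because tablet-based exclusions can reach only A and B, but its size and direction cannot be derived from the documents.

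For a single control comparison in stage 3, power is about 77% after one loss from a full control arm (10 vs 3) and about 61% at 9 vs 2, against the stated 80%. These figures rest on the plan's SD, effect and normality, on separate control arms, and on counting an exact p of 0.05 as a rejection at 9 vs 3 (14.4.3 asks for p below 0.05). The frequency of such exclusions is unknown; 5% to 20% is an assumed range. The point should be corrected, but it does not undermine the design.

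**What to change.** Reconcile 8.5, 8.6.1, 8.6.4, 9.5, 12.1.1, 12.1.2 and 14.4.3 so that stopping study drug is one decision, and ending follow-up and data use is another. In particular:

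- State that every treated participant is asked to attend the remaining visits, including days 10 and 28, subject to consent.
- State that available data stay in the safety set and the modified intention-to-treat efficacy set. This means changing the data cut-off in 12.1.2 and the exclusion of people who discontinue in 14.4.3. Rewording 8.5 and 8.6.1 alone would not restore the data.
- Record prohibited-medicine use and missed doses, and list them by arm.
- Make an analysis restricted by adherence or co-medication a sensitivity analysis.
- Reconcile the steroid entry in 8.6.1 with 7.2.21.

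Which medicines are prohibited and when dosing stops is for the sponsor to settle; nothing here depends on the answer.

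The cost is an amendment to wording, with no new visits or assays. The downside is that the primary set keeps a few under-dosed or co-medicated participants, which may slightly dilute the effect.
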